16.0 Potential Benefits to Subjects*

16.1 *Describe the potential benefits that individual subjects may experience from taking part in the research. Include as may be useful for the IRB's consideration, the probability, magnitude, and duration of the potential benefits.*

No direct benefit.

16.2 *Indicate if there is no direct benefit. Do not include benefits to society or others.*

No direct benefit.

17.0 Data Management* and Confidentiality

17.1 *Describe the data analysis plan, including any statistical procedures or power analysis.*

Data analysis will follow standard procedures detailed in the relevant literature including frequentist tests and Bayesian statistics when applicable. Power analyses will be performed on relevant past and/or

PROTOCOL TITLE: TMS Studies of Working Memory and Cognitive Control

preliminary data to inform planned sample sizes. If such data are not available, power analyses will be performed based on anticipated effect sizes.

17.2 *Describe the steps that will be taken to secure the data (e.g., training, authorization of access, password protection, encryption, physical controls, certificates of confidentiality, and separation of identifiers and data) during storage, use, and transmission.*

The steps that will be taken to secure the data (e.g., training, authorization of access, password protection, encryption, physical controls, certificates of confidentiality, and separation of identifiers and data) during storage, use, and transmission include retaining information in digital format. Digital information will be stored on password protected local machines, or on secure cloud based services such as Google Docs also requiring a password.

17.3 *Describe any procedures that will be used for quality control of collected data.*

NA

17.4 *Describe how data or specimens will be handled study-wide:*

- *What information will be included in that data or associated with the specimens?*
- *Where and how data or specimens will be stored?*
- *How long the data or specimens will be stored?*
- *Who will have access to the data or specimens?*
- *Who is responsible for receipt or transmission of the data or specimens?*
- *How data or specimens will be transported?*

NA

18.0 Provisions to Monitor the Data to Ensure the Safety of Subjects*

This section is required when research involves more than Minimal Risk to subjects.

18.1 *Describe:*

- *The plan to periodically evaluate the data collected regarding both harms and benefits to determine whether subjects remain safe. The plan might include establishing a data monitoring committee and a plan for reporting data monitoring committee findings to the IRB and the sponsor.*
- *What data are reviewed, including safety data, untoward events, and efficacy data.*

- *How the safety information will be collected (e.g., with case report forms, at study visits, by telephone calls with participants).*
- *The frequency of data collection, including when safety data collection starts.*
- *Who will review the data.*
- *The frequency or periodicity of review of cumulative data.*
- *The statistical tests for analyzing the safety data to determine whether harm is occurring.*
- *Any conditions that trigger an immediate suspension of the research.*

The primary safety risk of TMS is seizure. Any seizures resulting from TMS will be reported to the IRB. The incidences of seizures will be monitored. If it appears that the incidences of seizures observed in the study are statistically higher than those reported in the literature (e.g. through the use of a chi-square test), the IRB will be alerted and the safety protocol will be revisited.

19.0 Provisions to Protect the Privacy Interests of Subjects

19.1 *Describe the steps that will be taken to protect subjects' privacy interests. "Privacy interest" refers to a person's desire to place limits on whom they interact or whom they provide personal information.*

The steps taken to protect subjects' privacy interests include testing in a private and secure location requiring keycard access. Subjects will be consented and screened individually in a testing room, where he or she will have contact with trained personnel identified in this application. During the consenting process, the participant will only have contact with trained personnel identified in this application.

19.2 *Describe what steps you will take to make the subjects feel at ease with the research situation in terms of the questions being asked and the procedures being performed. "At ease" does not refer to physical discomfort, but the sense of intrusiveness a subject might experience in response to questions, examinations, and procedures.*

Subjects will be able to stop or leave at any moment. Additionally, trained personnel will deliver instructions and provide information regarding where to go if they have questions.

19.3 *Indicate how the research team is permitted to access any sources of information about the subjects.*

The research team is permitted to access any sources of information about the subjects using the digital formats storing subject information. Researchers will need to know the passwords or have access to view the information.

20.0 Compensation for Research-Related Injury

20.1 If the research involves more than Minimal Risk to subjects, describe the available compensation in the event of research related injury.

None

20.2 Provide a copy of contract language, if any, relevant to compensation for research-related injury.

Routinely, FSU, its agents, or its employees do not compensate for or provide free care for human subjects in the event that any injury results from participation in a research project. If you become ill or injured as a direct result of participating in this study, contact your regular medical provider. If you have insurance, your insurance company may or may not pay for these costs. If you do not have insurance, or if your insurance company refuses to pay, you will be billed. Funds to compensate for pain, expenses, lost wages and other damages caused by injury are not routinely available.

21.0 Economic Burden to Subjects

21.1 Describe any costs that subjects may be responsible for because of participation in the research.

NA

22.0 Consent Process

22.1 Consent will be obtained:

- In person, onsite in the [name] lab or [name] lab, prior to the collection of data.
- There will be no waiting period available between informing the prospective subject and obtaining consent.
- There will be no process to ensure ongoing consent
- HRP-090 consent will not be used.
- The individuals listed in the application will tell subjects that the purpose of the study is to understand the mental processes involved in retaining information in mind when it is no longer available to the senses, and using retained information to guide behavior. The participants will also be informed of the duration of the experiment, use of TMS, use of EEG, and inclusion and exclusion criteria.
- Additionally, participants will be screened in order to minimize risks associated with fMRI. Screening will proceed in two phases. First, the screening form will be sent to the participant via email (see Appendix). The participant will be asked to respond with whether the answer to any question on the screening form is “yes”. If the response is “yes” to any question, the participant will be excluded. If the participant

passes the first phase of screening and remains interested in participating, the participant will be invited to perform the study. Participants will read the consent form and any questions will be answered. After answering questions, the participant will once again be presented with the screening form. If the answer is “yes” to a given question, the participant may be asked to elaborate. A “yes” response may occur in the second screening, but not the first, if circumstances changed since the initial screening.

- Consent discussion will occur prior to data collection. Data collection will not occur until subjects understand the study outlines and protocol.
- Researchers will inform subjects that participation is voluntary and they can leave at any moment.
- Researchers will ask participants questions regarding understanding of the study before proceeding.
- The consenting process will take as long as any subject needs to understand the experiment.
- Steps that will be taken to minimize the possibility of coercion or undue influence include understanding the task and a formal signature on the consent document before proceeding with data collection.

Non-English Speaking Subjects

- NA

Waiver or Alteration of Consent Process (consent will not be obtained, required information will not be disclosed, or the research involves deception)

- NA

Subjects who are not yet adults (infants, children, teenagers)

- NA

Cognitively Impaired Adults

- NA

Adults Unable to Consent

- NA

Adults Unable to Consent

- NA

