
PROTOCOL TITLE: TMS Studies of Working Memory and Cognitive Control

following TMS, or both. The EEG assesses electrical brain activity through surface recording disks (electrodes) which are placed near the participant's head. The electrodes transmit the signals, which are then amplified (via an 8 channel Brain Vision LiveAmp) and stored on a computer. The procedure is entirely non-invasive.

An electrode cap will be placed on the participant's head. In order to record brain activity, these disks need to be filled with a gel which allows the electrodes to better record brain activity at the scalp.

Therefore, the participants in this study will need to clean their hair after participation. The gel is completely water soluble, and the procedure is painless. The MRI facility has sinks and towels, and the investigators will help to make sure the participant has thoroughly rinsed all the gel from their hair. After an accurate signal is assured, the signal derived from the electrode cap is then amplified, transmitted to a computer, and stored for later analysis.

In addition to the EEG recording, muscle activity from around the eyes may be recorded from the subjects. Muscle activity from around the eyes is recorded by two small sensors that will be placed below the participant's left eye, as well as behind the ears. These procedures are completely noninvasive and painless.

6.2 *Provide a description of all research procedures being performed and when they are performed, including procedures being performed to monitor subjects for safety or minimize risks.*

Below is a description of the kinds of tasks that participants may perform in a piecemeal fashion. It is likely that elements from multiple such tasks will be combined into a single task. Hereafter, stimuli will refer to letters, numbers, words, pictures, or sounds. Unless otherwise specified, stimuli will be affectively neutral. In general, tasks will range in duration from 5-10 minutes to 1-2 hours. Breaks will be given every 5-10 minutes. Multiple sessions may be performed. Based upon performance on the tasks, we may contact participants to perform other related tasks. Returning to perform other tasks will be optional and have no bearing upon the tasks the participants have already completed.

- Computer-based Tasks
 - Short-term memory

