 - a. Participants will be screened to be fluent in English, between the ages of 18-30, and to have no contraindications for TMS. Participants will also be screened such that they do not belong to populations vulnerable to the Coronavirus Disease (COVID-19) and have not been exposed. They will also be asked to indicate whether they have received

PROTOCOL TITLE: TMS Studies of Working Memory and Cognitive Control

a full FDA-authorized COVID-19 vaccination series, the specific vaccine product they received, and the date of complete vaccination.

- Demographics
 - a. Demographic information including age, gender, race, and ethnicity will be collected. This information will be used for reporting purposes to demonstrate fair inclusion. Participants will be informed that providing this information will be optional. This information has no direct bearing upon the research to be performed
- Follow-up Form
 - a. One month after the last TMS session, participants will be contacted and asked to fill out a follow-up form. This form inquires about possible experiences the participant may have had that may be attributable to TMS. This information will be used to assess any possible risks of TMS.

6.3 *Describe:*

- *Procedures performed to lessen the probability or magnitude of risks.*
- *All drugs and devices used in the research and the purpose of their use, and their regulatory approval status.*
- *The source records that will be used to collect data about subjects. (Attach all surveys, scripts, and data collection forms.)*

To lessen the probability or magnitude of risks, researchers will stop testing or administer breaks if participants feel frustrated, tired, and/or uncomfortable. Additionally, the occurrence of any adverse events associated with this study and its procedures, as well as any changes in risk level, will be monitored by the principal investigator and co-investigators.

The most severe risk is that of seizure. The risk of seizure will be minimized in two ways 1) Using stimulation parameters that are within the safety guidelines reported by Rossi et al., 2009, and 2) Excluding participants at increased risk for seizure as indicated in the exclusion criteria. Within the stimulation parameters to be used in the present protocol, no seizures have been reported resulting from TMS in the populations that we

PROTOCOL TITLE: TMS Studies of Working Memory and Cognitive Control

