For in-person study activities involving prospective subjects and study staff, we will as part of our screening and eligibility procedures implement the option of informing subjects and staff that their voluntary disclosure of their full COVID-19 vaccination status is an alternative to the requirement for COVID-19 precautions such as social distancing, use of masks, and other safety precautions. In doing so, we will use the following language: "In order to protect against COVID-19 or Coronavirus, if you come to the lab we are required to follow certain precautions like social distancing and use of masks. However, we don't have to do this for persons who have completed a full COVID-19 vaccination. You may if you'd like share with us information about your COVID-19 vaccination, but this is your decision and is not required. You can still come to the lab and we will follow our usual COVID-19 precautions."

PROTOCOL TITLE: TMS Studies of Working Memory and Cognitive Control

To implement this COVID-19 vaccination option, we will make a note in our study records for each prospective subjects and staff who choose to disclose their COVID-19 vaccination information.

6.4 *What data will be collected during the study and how that data will be obtained.*

The data that will be collected during the study includes identifying information. Additionally, brain activations, accuracies and reaction times to tasks will be collected. The data will be obtained using computerized-based tasks or written tasks.

6.5 *If there are plans for long-term follow-up (once all research related procedures are complete), what data will be collected during this period.*

In some cases, performance in some tasks will trigger eligibility for other tasks. In these cases, procedures will be identical to those described above.

6.6 *For Humanitarian Use Device (HUD) uses provide a description of the device, a summary of how you propose to use the device, including a description of any screening procedures, the HUD procedure, and any patient follow-up visits, tests or procedures.*

NA

7.0 **Data and Specimen Banking***

7.1 *If data or specimens will be banked for future use, describe where the specimens will be stored, how long they will be stored, how the specimens will be accessed, and who will have access to the specimens.*

NA

7.2 *List the data to be stored or associated with each specimen.*

NA

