9.0 Study Timelines*

9.1 Describe:

- *The duration of an individual subject's participation in the study.*
- *The duration anticipated to enroll all study subjects.*
- *The estimated date for the investigators to complete this study (complete primary analyses)*

The duration for each individual's participation will be between 1 and 2 hours per session. Participants will participate in at least 1, and potentially several sessions. It may take up to several weeks to complete an entire task. The duration anticipated to enroll all study subjects is 72 months.

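### The protocol rules out an ongoing-consent process although participants may return or be recalled, and no written step gives them new risk information

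*Combined protocol and SAP*

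**What the plan says.** Among the consent arrangements in section 22.1 of the combined protocol and SAP is the line "There will be no process to ensure ongoing consent". The same section places the consent discussion before data collection and has staff say that taking part is voluntary.

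On attendance, section 9.1 says: "Participants will participate in at least 1, and potentially several sessions". It adds: "It may take up to several weeks to complete an entire task". Section 6.2 allows recall: "Based upon performance on the tasks, we may contact participants to perform other related tasks". It also makes clear that "Returning to perform other tasks will be optional". Section 6.5 repeats the idea ("In some cases, performance in some tasks will trigger eligibility for other tasks") and says the procedures are then the same as in the main study. Section 13.5 provides for a completion bonus for paid participants in multisession studies.

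On risk, section 6.3 says that adverse events, "as well as any changes in risk level, will be monitored by the principal investigator and co-investigators". Section 18.1 says that if seizures look more frequent than in the literature, "the IRB will be alerted and the safety protocol will be revisited".

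**The concern.** Consent given once, before the first session, rests on what was known about risk on that day. The protocol expects that knowledge may move: it has the investigators watch for changes, collects a follow-up form one month after the last TMS session to assess possible risks, and foresees a review of its safety rules. It also allows the same person to be stimulated again later. A reader would then expect some step that brings new information to that person before the next stimulation. Section 22.1 disclaims the process in which such a step would sit.

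At stake is whether a returning participant has an informed occasion to reconsider. Someone who consented before a seizure occurred in the study could, under the text as written, attend a further session on the risk statement first given. This is a matter of participant protection; no estimate, test or sample size depends on it.

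**Working it through.** No arithmetic applies. The check sets the sections side by side and asks whether any of them connects new risk information to an enrolled participant.

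1. **Is there a stated rule?** Yes. The line in 22.1 is current text and is explicit. The point therefore does not rest on silence alone.

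2. **Can a participant be stimulated again after consent?** Yes, as a possibility. Section 9.1 sets a minimum of one session and allows several, spread over weeks. Sections 6.2 and 6.5 allow recall, and 13.5 budgets for multisession studies. The Study Summary gives 1-2 hours per participant, but 9.1 gives that figure per session. Repeat attendance is foreseen but is not the rule for everyone.

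3. **Does the protocol expect risk information to change?** Yes. Section 6.3 assigns the monitoring, 6.2 collects the one-month form, and 18.1 describes a trigger and a response. Section 6.1 also adopts theta-burst intensity limits by reference to a 2021 update of the safety guidelines, so guidance has moved before. Enrolment is planned over 72 months. That figure is the accrual period, during which information could change; it is not one person's exposure.

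4. **Where does the information go?**
   - Seizure during a session (6.3, 15.1): reported to the IRB.
   - Syncope (15.1): procedures end and the IRB is told.
   - Excess of seizures (18.1): the IRB is told and the safety rules are reviewed.
   - Other adverse events and changes in risk (6.3): watched by the investigators; no onward step is given.

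   None of these lines names participants who still have sessions to come.

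5. **Does another provision fill the gap?**
   - The right to leave at any time (19.2, 22.1) and the optional nature of recall (6.2) let a person decline, but do not tell that person what has changed.
   - The questions about discomfort (6.1, 6.3, 15.1) draw information from the participant rather than giving it.
   - The second screening (10.1, 22.1) is there because circumstances may have changed since the e-mailed form. It concerns the participant's eligibility, not the study's risk. It does show that the protocol treats even a short gap as worth a recheck.
   - The consent form (23.3) is attached to the application but was not in the text available for review, so nothing can be concluded about what it says. If it promises new information, staff following 22.1 have no step by which to deliver it, and the two texts must be reconciled.

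Result: in the available text, points 1 to 3 create the need for a step, and points 4 and 5 show none.

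**The case against.** The best defence is that the absence of a written route is not a rule against informing people. Alerting the IRB could lead to notification or re-consent, and a revised safety protocol would govern every later stimulation, including that of people already enrolled. Staff also stop or pause a session on discomfort, nobody is obliged to return, and the unseen consent form may deal with new findings. Section 15.1 expects few adverse effects at the planned settings.

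Much of this stands, and it limits what can be said. Four stronger readings are tempting, and the documents support none of them.

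- A reader might infer that a change in risk never reaches people still being stimulated. No section says so; the text only lacks a route.
- A reader might infer that the monitoring protects only people enrolled afterwards. It does not follow, because revised safety rules and the in-session safeguards apply to current participants too.
- A reader might infer that individuals move from lower-risk to higher-risk stimulation between sessions without fresh consent. Section 6.1 describes the modes by type of study, and no section says that one person passes from one mode to another. The remark in 15.1 that adverse effects rise with intensity, frequency and duration concerns protocols in the literature. Whether recall leads to new consent is unstated, not excluded.
- A reader might put a number on the people affected. The documents give no share with repeat sessions, and harm would also require new risk information to arise between one person's sessions.

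What the defence does not remove is the explicit line in 22.1. A possible decision by the IRB is not a study procedure, and a freedom to leave is of limited use to someone who has not been told what is new.

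**Conclusion.** The point holds in limited form. The protocol disclaims ongoing consent while allowing repeat sessions and recall and while monitoring for changed risk, and its available text contains no step that informs returning participants or reconfirms their agreement. Section 22.1 should be reconciled with 6.2, 6.3, 6.5, 9.1, 13.5 and 18.1.

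The conclusion rests on two conditions: that at least some participants do attend more than once, which the protocol allows but does not quantify, and that the judgement is confined to the text available, without the consent form. It makes no claim about how often risk information will change. It is an inexpensive improvement in participant protection and not a threat to the validity of the study.

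**What to change.** Three changes to the text:

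- **Section 22.1.** Replace the line on ongoing consent with a brief documented check at the start of every session after the first and at any recall. Staff pass on any risk information that is new since consent, and the participant confirms willingness to continue.
- **Section 18.1.** Add that when a change in risk is reported to the IRB, participants with sessions outstanding are told before their next session.
- **Recall.** If a recall uses a type of stimulation that the first consent did not cover, obtain consent to it in general terms, without announcing the expected direction of effect or the condition of that session.

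The last restriction protects the data. Outcomes are accuracy and speed compared across TMS parameters (6.1), and offline stimulation is meant to lower or raise performance. Announcing the mode at each session could therefore create expectancy effects. Passing on new risk information does not require it.

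The consent form should be checked against the new wording so that the two agree.

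The cost is an estimated 1-2 minutes per repeat session and possibly a few participants who decline to go on. No stimulation setting, clinical rule or statistical figure changes.
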